9. STATISTICAL CONSIDERATIONS

Methodology for summary and statistical analyses of the data collected in this study is described here and further detailed in a statistical analysis plan (SAP), which will be maintained by the sponsor. The SAP may modify what is outlined in the protocol where

PFIZER CONFIDENTIAL

appropriate; however, any major modifications of the primary endpoint definitions or their analyses will also be reflected in a protocol amendment.

9.1. Estimands and Statistical Hypotheses

9.1.1. Estimands

The estimands corresponding to each objective are described in the table in [Section 3](#). The estimands to evaluate the immunogenicity objectives for NI are based on evaluable populations (see [Section 9.3](#) for definition). These estimands estimate vaccine effect in the hypothetical setting where participants follow the study schedules and protocol requirements as directed. The estimand addresses the objective of estimating the maximum potential difference between 2 groups, since the impact of noncompliance is likely to diminish the observed difference between the 2 groups. Missing serology results will not be imputed. Immunogenicity results that are below the LLOQ will be set to $0.5 \times \text{LLOQ}$ in the analysis.

In the primary safety objective evaluations, missing e-diary data will not be imputed. Missing AE dates will be imputed according to Pfizer safety rules. No other missing information will be imputed in the safety analysis.

The endpoints and estimands corresponding to the objectives for the Russian cohort can be found in [Section 10.10.3](#). All the statistical analysis for the Russian cohort will be descriptive.

9.1.2. Statistical Hypotheses

All hypothesis testing will be performed on the data from the primary study population.

9.1.2.1. Pneumococcal Immunogenicity Hypotheses

9.1.2.1.1. Percentage of Participants With Predefined Pneumococcal Serotype-Specific IgG Concentrations 1 Month After Dose 2

Hypothesis testing will be used to assess the NI of 20vPnC to 13vPnC for the percentage of participants with predefined pneumococcal serotype-specific IgG concentrations 1 month after Dose 2. The null hypothesis (H_{0A}) for a serotype is

$$H_{0A}: \pi_{20vPnC} - \pi_{13vPnC} \leq -10\%,$$

with a 10% margin for NI, where

- π_{20vPnC} is the percentage of participants achieving an IgG antibody concentration of predefined level in the 20vPnC group for the serotype 1 month after Dose 2;
- If the serotype is from the 13 matched serotypes (1, 3, 4, 5, 6A, 6B, 7F, 9V, 14, 18C, 19A, 19F, 23F) in 13vPnC, π_{13vPnC} is the percentage of participants achieving a predefined IgG concentration for the serotype from the 13vPnC group 1 month after Dose 2;

- If the serotype is from the 7 additional serotypes (8, 10A, 11A, 12F, 15B, 22F, 33F) in 20vPnC, π_{13vPnC} is the percentage of participants achieving a predefined IgG concentration from the serotype with the lowest percentage among the 13 serotypes from the 13vPnC group 1 month after Dose 2, provided that the lowest percentage is not from serotype 3. If the lowest percentage in the 13vPnC group is from serotype 3, the next lowest percentage in the 13vPnC group will be used in the comparison. Historical data suggest that serotype 3 behaves somewhat differently from the other serotypes in 13vPnC; therefore, IgG results from serotype 3 will not be used in the comparison to assess the NI of the 7 additional serotypes;
- The predefined levels for serotype-specific IgG concentrations are 0.35 $\mu\text{g/mL}$ for all serotypes in 20vPnC except that the predefined levels are 0.23 $\mu\text{g/mL}$, 0.10 $\mu\text{g/mL}$, and 0.12 $\mu\text{g/mL}$ for serotypes 5, 6B, and 19A, respectively.

The null hypothesis (H_{0A}) will be rejected and NI of 20vPnC to 13vPnC for the percentage of participants with predefined IgG concentration for a serotype will be declared if the lower bound of the 2-sided 95% CI for the difference (20vPnC – 13vPnC) in percentages, computed using the Miettinen and Nurminen method, is greater than –10% (10% NI margin).

9.1.2.1.2. Pneumococcal Serotype-Specific IgG GMCs 1 Month After Dose 2

Hypothesis testing will be used to assess the NI of 20vPnC to 13vPnC for pneumococcal serotype-specific IgG GMCs 1 month after Dose 2. The null hypothesis (H_{0B}) for a serotype is

$$H_{0B}: \ln(\mu_{20vPnC}) - \ln(\mu_{13vPnC}) \leq \ln(0.5)$$

where $\ln(0.5)$ corresponds to a 2-fold margin for NI and

- $\ln(\mu_{20vPnC})$ is the natural log of the geometric mean IgG concentration in the 20vPnC group for that serotype 1 month after Dose 2;
- If the serotype is from the 13 matched serotypes (1, 3, 4, 5, 6A, 6B, 7F, 9V, 14, 18C, 19A, 19F, 23F), $\ln(\mu_{13vPnC})$ is the natural log of the geometric mean IgG concentration in the 13vPnC group 1 month after Dose 2;
- If the serotype is from the 7 additional serotypes (8, 10A, 11A, 12F, 15B, 22F, 33F) in 20vPnC, $\ln(\mu_{13vPnC})$ is the natural log of the geometric mean IgG concentration for the serotype with the lowest IgG GMC among the 13 serotypes from the 13vPnC group 1 month after Dose 2, provided that the lowest GMC is not from serotype 3. If the lowest GMC in the 13vPnC group is from serotype 3, the next lowest GMC in the 13vPnC group will be used in the comparison. As stated in [Section 9.1.2.1.1](#), historical data suggest that serotype 3 behaves somewhat differently from the other serotypes in 13vPnC; therefore, IgG results from serotype 3 will not be used in the comparison to assess the NI of the 7 additional serotypes.

The null hypothesis (H_{0B}) will be rejected and NI of 20vPnC to 13vPnC for the pneumococcal serotype-specific IgG GMC will be declared for a serotype if the lower bound of the 2-sided 95% CI for the IgG GMR of 20vPnC to 13vPnC is greater than 0.5 (2-fold NI margin).

9.1.2.1.3. Pneumococcal Serotype-Specific IgG GMCs 1 Month After Dose 3

Hypothesis testing to assess the NI of 20vPnC to 13vPnC for pneumococcal serotype-specific IgG GMCs 1 month after Dose 3 will be performed similarly to that for IgG GMCs 1 month after Dose 2, as described in [Section 9.1.2.1.2](#), with $\ln(\mu_{20vPnC})$ and $\ln(\mu_{13vPnC})$ being the natural log of the geometric mean IgG concentrations 1 month after Dose 3 from the 20vPnC and 13vPnC groups, respectively, except for the 7 additional serotypes in 20vPnC, where $\ln(\mu_{13vPnC})$ is the natural log of the geometric mean IgG concentration for the serotype with the lowest IgG GMC among the 13 serotypes from the 13vPnC group, provided that the lowest GMC is not from serotype 3. If the lowest GMC in the 13vPnC group is from serotype 3, the next lowest GMC in the 13vPnC group will be used in the hypothesis testing.

The null hypothesis (H_{0C} : $\ln[\mu_{20vPnC}] - \ln[\mu_{13vPnC}] \leq \ln[0.5]$) will be rejected and NI of 20vPnC to 13vPnC for the pneumococcal serotype-specific IgG GMC will be declared for a serotype if the lower bound of the 2-sided 95% CI for the IgG GMR of 20vPnC to 13vPnC for the serotype is greater than 0.5 (2-fold NI margin).

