9.1.3. Multiplicity Consideration

Primary Pneumococcal Immunogenicity Evaluation

For the primary pneumococcal immunogenicity objectives comparing serotype-specific IgG concentrations from the 20vPnC group to that from the 13vPnC group, NI of the immune response for each serotype is assessed by the hypothesis tests as described in [Section 9.1.2.1.1](#) and [Section 9.1.2.1.2](#), each at an alpha level of 0.05. The primary pneumococcal immunogenicity objectives will be achieved if NI of the immune response induced by 20vPnC compared to 13vPnC based on both percentages of participants with predefined IgG levels and IgG GMCs at 1 month after Dose 2, as well as the IgG GMCs at 1 month after Dose 3, is established for all 20 serotypes, a total of 60 NI evaluations. Therefore, the overall type I error rate for the primary immunogenicity assessment of the pneumococcal immune response of 20vPnC 1 month after Dose 3 is well controlled at the 0.05 level.

Primary Concomitant Immunogenicity Evaluation

All the primary concomitant immunogenicity endpoints/estimands are considered coprimary in the study. For the primary concomitant immunogenicity objective comparing immune responses induced by concomitant vaccine antigens from the 20vPnC group to that from the 13vPnC group, NI is assessed by hypothesis tests as stated in [Section 9.1.2.2](#), at a significance level of 0.05 for each of the concomitant vaccine antigens, including diphtheria toxoid, tetanus toxoid, PT, FHA, PRN, HBsAg, poliovirus strains, Hib, measles, mumps, rubella, and varicella. The primary concomitant immunogenicity objective will be met if NI is achieved for each concomitant vaccine antigen. Therefore, the type I error rate for the concomitant immunogenicity assessment is well controlled at the 0.05 level.

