9.2. Sample Size Determination

The sample size of the study is determined primarily based on considerations of 1) accumulating a sufficient overall safety database for the 20vPnC infant clinical development program, 2) providing robust assessment of the pneumococcal immune responses induced by 20vPnC and 13vPnC, 3) ensuring robust assessment to demonstrate that the immune responses induced by concomitant vaccine antigens given with 20vPnC are noninferior to immune responses induced by concomitant vaccine antigens given with 13vPnC, and 4) practical constraints of available serum volumes from individual study participants with all planned immunogenicity assessments.

9.2.1. Sample Size Consideration for the Primary Pneumococcal Immunogenicity Objectives for the Primary Study Population

The study power for the primary pneumococcal immunogenicity objectives is assessed based on simulations of multivariate log-normal distributed random numbers with assumptions supported by IgG results after 2 and/or 3 infant doses from historical 13vPnC and 7vPnC infant studies, and IgG results after 3 infant doses and the toddler dose of an internal Phase 2 infant study of 20vPnC (B7471003).

For the immune response 1 month after 2 infant doses of 20vPnC, serotype-specific IgG GMCs and the variance-covariance matrix are assumed to be the same as those estimated from Study B7471003 1 month after 3 infant doses of 20vPnC, after adjustments made based on the observed relationship between IgG results after 2 infant doses and after 3 infant doses in the historical studies. To accommodate the uncertainties in the assumptions, 3 different assumed GMRs of the 20vPnC to the 13vPnC group 1 month after Dose 2 are explored to evaluate the study power in the simulation **CCI**

For the immune response 1 month after Dose 3 (toddler dose), the true GMCs and variance-covariance matrices for the 20 serotype-specific IgG concentrations from both the 20vPnC and 13vPnC groups are assumed to be the same as the IgG results 1 month after Dose 4 from Study B7471003 (3 infant doses and a toddler dose).

With approximately 1200 enrolled participants using a 1:1 randomization ratio, assuming a 10% nonevaluable rate at 1 month after Dose 2, and a 17% nonevaluable rate at 1 month after

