Dose 3, the study will result in approximately 540 and 500 evaluable participants for each vaccine group at 1 month after Dose 2 and 1 month after Dose 3, respectively. Under the 3 IgG GMR assumptions, the study has approximately 99%, 97%, and 85% probability, respectively, to show NI of 20vPnC to 13vPnC for at least 47 (out of 60 total) positive NI assessments comparing IgG results CCI | CCI

CCI

CCI

CCI

CCI

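### Does testing the 7 additional serotypes against the lowest 13vPnC result seen in the trial undo the error control claimed in Protocol 9.1.3?

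*Protocol*

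**What the plan says.** Protocol 9.1.2.1 sets three primary tests for each additional serotype: the percentage reaching the reference concentration after Dose 2, the GMC after Dose 2 and the GMC after Dose 3. The comparator is not named in advance. For percentages it is defined as "lowest percentage among the 13 serotypes from the 13vPnC group 1 month after Dose 2, provided that the lowest percentage is not from serotype 3". For the Dose 2 GMC it is "the serotype with the lowest IgG GMC among the 13 serotypes from the 13vPnC group 1 month after Dose 2", again passing over serotype 3: "If the lowest GMC in the 13vPnC group is from serotype 3, the next lowest GMC in the 13vPnC group will be used". The same GMC rule applies after Dose 3. Intervals are ordinary Miettinen-Nurminen for percentages and t-based for GMCs (SAP 5.2.1 and 5.2.2.2).

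Protocol 9.1.3 says the primary pneumococcal objectives are met if noninferiority "is established for all 20 serotypes, a total of 60 NI evaluations". From this it infers that the overall type I error for the assessment of "20vPnC 1 month after Dose 3 is well controlled at the 0.05 level".

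Sample size (Protocol 9.2.1) rests on "simulations of multivariate log-normal distributed random numbers with assumptions supported by IgG results". For the toddler dose, GMCs and covariances are "assumed to be the same as the IgG results 1 month after Dose 4 from Study B7471003". The assumed serotype values are blacked out. The visible power statement gives the chance "to show NI of 20vPnC to 13vPnC for at least 47 (out of 60 total) positive NI assessments".

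**The concern.** Requiring every test to pass controls the overall error only if each component test is itself valid at its level. Here 21 of the 60 use a comparator chosen by looking at which eligible 13vPnC serotype came out lowest. A standard interval treats that serotype as fixed beforehand. If several serotypes truly share the lowest response, the smallest observed value tends to fall below the true minimum. The bar is then a little too low, and an additional serotype lying exactly on the margin passes more often than intended.

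At stake is the noninferiority claim for the 7 new serotypes, which are the reason for the vaccine. The Dose 3 GMC tests look most exposed, because the Dose 3 percentage is only descriptive and gives no second primary test at that visit. Protocol 9.1.3 states error control without any condition, and neither document shows that these 21 tests hold their level.

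**Working it through.** **Inputs from the documents.** 20 serotypes × 3 endpoints = 60 tests; 7 × 3 = 21 use the observed-lowest comparator and 13 × 3 = 39 do not. Candidate comparators: 13 − 1 (serotype 3) = 12. Evaluable per group: 600 × 0.90 = 540 after Dose 2; 600 × 0.83 = 498, stated as about 500, after Dose 3. Margins: −10 points and a GMR of 0.5. A test passes when the lower bound of a 2-sided 95% CI clears the margin, which is 2.5% in the noninferiority direction.

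**Assumptions.** Number of tied serotypes, spacing, within-child correlation (0.4 unless stated), ln SD of 1, and lowest rates of 80–95%. Least favourable case: one additional serotype exactly on the margin, the other 59 tests certain to pass.

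**The plan's own figure.** With a comparator fixed in advance, the GMC test at the margin has error Φ(−1.96) = 0.025. Simulating the Miettinen-Nurminen test at n = 540 gives 0.0249–0.0253 (lowest rates 75–90%). Requiring all 60 then keeps the overall error at or below that, so 9.1.3 is right for a named comparator.

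**Formula for the observed minimum (GMC).** In units of one arm's standard error, let x be the additional serotype's estimate measured from the margin and y_j the comparators, with gaps g_j above the true lowest and common correlation ρ. The test passes if any y_j < x − 1.96√2. With U distributed N(0, 1+ρ):

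error = 1 − E[ ∏ {1 − Φ((U − 1.96√2 − g_j)/√(1−ρ))} ].

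For one comparator this returns 0.025.

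**Exact ties, one-sided error.**

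| Tied lowest serotypes | 1 | 2 | 3 | 5 | 12 |
|---|---|---|---|---|---|
| Dose 3 GMC, ρ = 0.4 | 2.5% | 4.2% | 5.5% | 7.4% | 11.6% |

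For 12 tied GMCs the figure is 16.0% at ρ = 0 and 5.2% at ρ = 0.9. For Dose 2 percentages at correlation 0.4, two tied give 4.3 / 4.3 / 3.9% at lowest rates of 80 / 90 / 95%. Three tied give about 5.6% at 80% and 4.8% at 95%.

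**Even spacing between successive serotypes.** One arm's standard error is 1/√500 = 0.0447 on the log scale, so 2%, 5% and 10% GMC steps are ln(1.02)/0.0447 = 0.44, ln(1.05)/0.0447 = 1.09 and ln(1.10)/0.0447 = 2.13 standard errors.

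| Spacing | Error |
|---|---|
| GMC, 2% steps | 3.2–3.4% |
| GMC, 5% steps | about 2.6% |
| GMC, 10% steps | about 2.5% |
| Percentage, 3–5 serotypes from 80%, half-point steps | 4.0–4.1% |
| Same, 1-point steps | 3.1% |
| Same, 2-point steps | 2.6–2.7% |

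**A cluster just above the lowest.** If the other 11 all sit at one common distance above a lowest rate of 85%, and serotypes are independent, the error is 6.6% at 1 point, 3.6% at 2, 2.7% at 3 and 2.5% at 5. Twelve serotypes within a point of each other therefore behave like a tie.

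**Overall objective.** If the other 59 tests pass with probability q, independently, the error is multiplied by q. For three tied GMCs, 5.5% falls to 5% at q = 5/5.5 = 0.91 and to about 2.5% at q = 0.45.

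**The case for a change.** The strongest case for acting is that the statement in 9.1.3 is unconditional while the property is not, and that the sponsor already has the simulation to settle it. Two points add weight. Noninferiority is also declared serotype by serotype, and the power statement counts individual passes; at that level the all-60 requirement gives no protection and the single-test figures apply. Also, if 0.05 is read as two-sided, the one-sided benchmark is 2.5%, and even a two-way tie exceeds it.

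The logic stands, and so does the 2.5% reading. What does not follow is a defect in the plan. The error claim in 9.1.3 concerns the joint objective. There, a serotype with half the comparator's GMC after Dose 3 must also pass both Dose 2 tests, and the other tests will not pass with certainty. The remedy on offer is thin: a caveat that the lowest serotypes should not be nearly tied has no threshold and no consequence, and an extra simulation would show the error only at the sponsor's assumed values.

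A real statistical correction would cost more than it gains. Testing at 0.025/12 brings 12 independent tied GMCs to 1.9%. When one serotype is clearly lowest it cuts the level to 0.025/12 = 0.21%, for a problem that is then absent. Naming a comparator in advance restores 2.5% but gives up the rule of comparing with the lowest response.

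**Conclusion.** No change to the plan. The observed-lowest rule is fixed in advance, leaves the analyst no choice, and is a fair trade-off. Its cost is a modest optimism that depends on spacing: about 3–4% instead of 2.5% for evenly spaced serotypes at 2% GMC steps or half-point to one-point percentage steps, and close to nominal at 5% GMC steps or 2-point steps. The stated 0.05 is exceeded only with three or more essentially tied lowest serotypes, or with most of the 12 bunched within about a point, and then only if nearly all other tests pass. The documents show neither pattern; with the inputs blacked out it cannot be excluded, and that gap is not a fault of the plan. The 39 matched-serotype tests are unaffected.

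The reader of the results will be able to judge the spacing directly, because SAP 6.1.2.1.1 and 6.1.2.2.1 report every serotype's percentage and GMC with its interval in both groups.

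The objectives and estimands in Protocol 1.1 and 3 and SAP Table 2 omit the serotype 3 exclusion. That is a clerical slip: Protocol 9.1.2.1 and 9.4.1 and SAP 5.1.1 and 6.1.2 state it, so the analysis is not in doubt.

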9.1.2.2. Concomitant Immunogenicity Hypotheses

9.1.2.2.1. Noninferiority for Percentage of Participants With a Prespecified Antibody Level to Each Concomitant Vaccine Antigen 1 Month After Dose 3

Hypothesis testing will be used to assess the NI of the 20vPnC group to the 13vPnC group for the percentage of participants with a prespecified antibody level to each concomitant vaccine antigen at 1 month after Dose 3. The null hypothesis (H_{0C}) for each concomitant vaccine antigen is

$$H_{0C}: \pi_{20vPnC} - \pi_{13vPnC} \leq -10\%$$

with a 10% margin for NI, where π_{20vPnC} and π_{13vPnC} are the percentages of participants with prespecified antibody levels to diphtheria toxoid, tetanus toxoid, pertussis antigens (PT, FHA, PRN), HBsAg, poliovirus strains, or Hib at 1 month after Dose 3, from the 20vPnC group and the 13vPnC group, respectively.

The following are the prespecified antibody thresholds for the concomitant vaccine antigens:

Antigen	Prespecified Level
Diphtheria	≥ 0.1 IU/mL
Tetanus	≥ 0.1 IU/mL
Acellular pertussis (PT, FHA, PRN)	\geq the observed antipertussis antibody concentration achieved by 95% of 13vPnC recipients

PFIZER CONFIDENTIAL

Antigen	Prespecified Level
Hepatitis B	≥ 10 mIU/mL
Poliomyelitis (types 1, 2 and 3)	$\geq 1:8$
Hib	≥ 0.15 $\mu\text{g/mL}$ anti-PRP Alternative: ≥ 1.0 $\mu\text{g/mL}$ anti-PRP

The null hypothesis (H_{0C}) testing for NI will be rejected for a concomitant vaccine antigen if the lower bound of the 2-sided 95% CI for the difference (20vPnC – 13vPnC) in percentages, computed using the Miettinen and Nurminen method, is greater than –10% (10% NI margin).

9.1.2.2.2. Noninferiority for GMCs of Antibody Levels to Concomitant Vaccine Antigens 1 Month After Dose 3

Hypothesis testing will be used to assess the NI of the 20vPnC group to the 13vPnC group for GMCs of antibody levels to each concomitant vaccine antigen 1 month after Dose 3. The null hypothesis (H_{0D}) for each concomitant vaccine antigen is

$$H_{0D}: \ln(\mu_{20vPnC}) - \ln(\mu_{13vPnC}) \leq \ln(0.5)$$

where $\ln(0.5)$ corresponds to a 2-fold margin for NI, and $\ln(\mu_{20vPnC})$ and $\ln(\mu_{13vPnC})$ are the natural log of the GMCs for antibody levels to measles, mumps, rubella, and varicella virus at 1 month after Dose 3 from the 20vPnC group and the 13vPnC group, respectively.

The null hypothesis (H_{0D}) testing for NI will be rejected for a concomitant vaccine antigen if the lower bound of the 2-sided 95% CI for the GMR of GMCs (20vPnC over 13vPnC) is greater than 0.5 (2-fold NI margin).

